the 90-day FU to assess YMSM's satisfaction with the intervention, including the content, site layout and design, and general satisfaction. These domains are assessed on a 4-point response scale with individually specified anchors. The CSQ-8 has demonstrated high internal consistency across a large number of studies⁹⁵. The SEF and CSQ will take approximately 10 minutes to complete. We will also track users' actions in the intervention as process evaluation data. These data will include the number of times that they visited the site, their geographic location and the website from which they linked to our site, time spent in each session, number of times a user returns to a session, and which interactive features were "clicked on" during sessions.

Behavioral Assessments. The web surveys will be programmed to minimize out-of-range or inconsistent responses. Data exports will be automated into SPSS. The survey will be designed using best practices to encourage completion⁹⁶. Planned domains are listed below and may be refined based on the intervention content developed and YAB feedback. Based on our prior success in recruiting YMSM to complete online surveys, we will use best practices (e.g., surveys are dynamic and take less than 30 minutes to complete) to reduce participant burden. We have used all measures previously; scales have strong psychometric properties (i.e., adequate factor structure and $\alpha > .65$). Table 3 documents when domains will be assessed.

Table 3. Assessment Summary Table	BL	FU1	FU2	FU3
Sociodemographic Information				
Demographic data (e.g., race, sexuality)	X			
Social media use	X			
Changes in relationship, housing, work	X	X	X	X
Outcome indicators				
Sexual behavior	X	X	X	X
Recent HIV/STI test	X	X	X	X
Substance use	X	X	X	X
Predictors of Behavior Change				
TPB Constructs	X	X	X	X
Affective Motivations	X	X	X	X
Partner-seeking behaviors	X	X	X	X
Psychological Risk Correlates	X	X	X	X

information.

Outcome indicators: Consistent with our model, we have 3 primary risk reduction outcomes: increased consistent condom use across partner types (continuous), reduced number of UAI partners and occasions (continuous), and increased HIV/STI testing rates (dichotomous). We detail their assessment below:

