In exploratory analyses, we will use structural equation modeling (SEM¹¹⁴) to examine our model's adequacy to predict behavior change. Using our theoretically informed model (see Figure 2) as a blueprint¹¹⁵, these SEM analyses will help us begin to unpack what theoretical constructs and pathways were influential in YMSM's behavior change, and aid us to refine our conceptual model for the larger RCT. For example, we will test the hypothesis that cognitive (e.g., attitudes, norms, behavioral control) and affective factors (e.g., anticipated regret, decisional balance) independently contribute to the behavioral outcomes through behavioral intention. We will examine the Lagrange Multiplier and Wald Tests to consider the deletion or inclusion of paths¹¹⁶; ultimately, however, the deletion or inclusion of paths will be informed by theoretical underpinnings. Once the model is identified, we will test for group differences (i.e., MEET-ME vs NTHP) in latent constructs and in the paths between these constructs (e.g., intention to use condoms, consistent condom use). This method will allow us to estimate the intervention effects on the constructs directly as well as their relationships to one another¹¹⁷. We will follow guidelines for adequate reporting of SEM using three goodness-of-fit indices: Bentler-Bonnet's Normed Fit Index (NFI), Bentler-Bonnet's Non-Normed Fit Index (NNFI), and the Comparative Fit Index (CFI). We will also verify the root mean-square error of approximation (RMSEA) as an index of misfit. Well-fitting models will have fit indices of .90 or higher and $<.06$ for RMSEA. **Power for secondary analysis:** SEM power calculations are computed by estimating the best fit for a full latent model. Based on calculations provided by MacCallum, we have ample statistical power given the repeated measures design¹¹⁸ (e.g., 80% power is achievable with $\alpha=.05$ & 95 df with a N=180 for close model fit, where null RMSEA value is .05 and the alternate value is .08).

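### The SEM fit rule holds the uncorrected Normed Fit Index to the same .90 cut-off as NNFI and CFI, so an adequate model can be labelled poorly fitting if the constructs are only modestly reliable

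*Combined protocol and SAP*

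**What the plan says.** The exploratory SEM paragraph, at the end of the data analysis text, lists "three goodness-of-fit indices: Bentler-Bonnet's Normed Fit Index (NFI), Bentler-Bonnet's Non-Normed Fit Index (NNFI), and the Comparative Fit Index (CFI") and adds RMSEA as an index of misfit. The standard follows: "Well-fitting models will have fit indices of .90 or higher". For RMSEA the requirement is a value below .06. Nothing exempts NFI or allows for sample size.

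The same paragraph says of model modification: "We will examine the Lagrange Multiplier and Wald Tests to consider the deletion or inclusion of paths". That sentence goes on to say that theory will have the final word on such changes.

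The only indication of model size is the example under Power for secondary analysis: "80% power is achievable with $\alpha=.05$ & 95 df with a N=180 for close model fit". That example tests an RMSEA of .05 against one of .08. The numbers of factors and indicators and the loadings are not given.

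On reliability, Behavioral Assessments states that "scales have strong psychometric properties (i.e., adequate factor structure"), with a floor for alpha of .65. The one value given for an individual scale is .82, for decisional balance, under Affective Motivations. The Phase 3 Recruitment text plans for 180 men and projects 20% attrition by 90 days.

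**The concern.** NNFI and CFI set the model chi-square against its degrees of freedom. NFI does not: it counts all of the model chi-square as misfit, including the amount expected from sampling error when the model is true. In a small sample with moderate correlations among indicators, the null-model chi-square is modest and that expected amount is a large share of it. NFI is then well below 1 even for a perfect model.

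The SEM is meant to judge whether the conceptual model is adequate and to refine it for the larger trial. If a correct model is labelled as failing, that step gives a wrong answer and may prompt needless respecification.

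**Working it through.** **The plan's own SEM figure.** For the close-fit test the noncentrality is (N − 1) × df × RMSEA². With N = 180 and 95 df this is 179 × 95 × .05² = 42.5 under the null and 179 × 95 × .08² = 108.8 under the alternative. At alpha .05 the power is 0.917, and 80% is already reached at N = 137. The stated 80% is therefore met as a lower bound but not reproduced as a point value. The gap is conservative and does not bear on the fit rule.

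**Inputs from the documents.** Cut-off .90 for all three indices and RMSEA below .06; about 95 df; N = 180; 180 × 0.8 = 144 if attrition leaves only complete cases (derived, not stated); alpha floor .65; single stated alpha .82.

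**Assumed, because not in the documents.** One pooled group, multivariate normal data, 16 indicators, four factors with four indicators each, and factor correlations of about .3 to .6. The df are 16 × 17/2 − 16 loadings − 16 residual variances − 6 correlations = 98. Five factors give 94 df and six give 89. Each loading is the square root of r = alpha / (k − (k − 1) × alpha). For k = 4, r is .65/2.05 = .32 at alpha .65, .75/1.75 = .43 at .75, and .82/1.54 = .53 at .82.

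**Threshold.** NFI = 1 − T/T0, where T is the model chi-square and T0 the null-model chi-square. NFI ≥ .90 requires T0 ≥ 10 × T. A correct model has expected T near its df, so at 95 df T0 must be about 950.

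**Simulation with the model exactly true** (maximum likelihood, 800 samples per row, four factors, factor correlation .3):

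| alpha | N | mean T | mean T0 | mean NFI | NFI below .90 | NNFI, CFI or RMSEA fails |
|---|---|---|---|---|---|---|
| .65 | 144 | 102.4 | 424 | .757 | 100% | 6.9% |
| .65 | 180 | 101.5 | 499 | .795 | 100% | 2.8% |
| .75 | 144 | 102.6 | 648 | .841 | 99.5% | 1.1% |
| .75 | 180 | 101.7 | 779 | .869 | 94.5% | 0.2% |
| .82 | 144 | 102.7 | 927 | .889 | 74.1% | 0.5% |
| .82 | 180 | 101.8 | 1127 | .909 | 23.6% | 0% |

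Across runs of the four-factor layout with different factor correlations, the miss rates are about 100% at alpha .65 and 72–100% at .75. At .82 they are 8–25% with N = 180 and about 50–77% with N = 144. At .90 the index almost never misses.

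**Why only NFI fails.** Take the mean values at alpha .65 and N = 180; the null model has 120 df.

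- NFI = 1 − 101.5/498.5 = .80.
- CFI = 1 − (101.5 − 98)/(498.5 − 120) = .99.
- NNFI = (498.5/120 − 101.5/98)/(498.5/120 − 1) = .99.
- RMSEA = √[(101.5 − 98)/(98 × 179)] = .014.

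**Other layouts** (miss rate at N = 144 / N = 180):

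- Five factors, correlation .3: 100% / 100% at alpha .65, 98% / 83% at .75, 48% / 8% at .82.
- Five factors, correlation .5: 100% / 99.8%, 92% / 58% and 29% / 2% at the same alphas.
- Six factors, correlation .3: 100% / 99.6% at .65 and 31% / 4% at .82.
- Five factors at alpha .90: 0% / 0%.
- Each indicator itself has reliability .65 and loads at √.65 = .81: 11% / 0%.

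**The case against.** The strongest objection is that the measurement model is the reviewer's and not the plan's. The 95 df is an example, and the miss rate runs from 0% to 100% across layouts that the documents permit. If the indicators were four waves per construct with the within-subject correlation of .6 from the power section, NFI passes in 100% of samples at N = 180 and 76–86% at N = 144. With the .4 that Table 4 also considers, it passes in only 0–4%. This objection stands, and the result has to be stated as conditional. The layouts nevertheless follow one pattern. Four indicators correlating .6 form a composite with alpha 4 × .6/(1 + 3 × .6) = .86; at .4 it is 1.6/2.2 = .73; four indicators each with reliability .65 give 2.6/2.95 = .88. High composite reliability rescues NFI and modest reliability does not.

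Two further objections also stand. The .65 is a floor across scales, and no scale is reported at that value. N = 144 assumes complete-case SEM, which the plan does not specify.

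A reader might infer that a low NFI will lead the team to add chance paths through Lagrange Multiplier tests. The documents do not support that. They do not make NFI a trigger for those tests, and the same sentence makes theory the final arbiter of path changes.

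A reader might also infer that the rule rejects correct models by construction. It does not. It labels fit and attaches no stated action, the other indices are reported beside it, and at the one stated alpha (.82) with N = 180 a correct four-factor model passes NFI in about 75–92% of samples.

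What survives is that the rule as written makes no exception for NFI, and that in plausible layouts NFI alone contradicts the other three indices when the model is true.

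**Conclusion.** The point holds as a conditional weakness in the fit rule. Under the assumed single-group, 16-indicator layouts, a correct model is very likely to miss NFI .90 when constructs have alpha of about .65 to .75. At .82 the risk is modest with all 180 men and substantial with 144 complete cases; at .90 it is negligible. CFI, NNFI and RMSEA each pass in about 93–100% of the same four-factor samples, so the failure belongs to NFI and not to the model or the data.

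The rates depend on a measurement model that the plan does not give and on multivariate normal data. They do not cover the planned comparison of paths between arms.

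The consequence is limited to how fit is described, and possibly to needless respecification, in an analysis labelled exploratory. No primary outcome, feasibility or acceptability result depends on it. Severity is minor.

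**What to change.** Remove NFI from the fit rule; it may still be reported descriptively. Judge fit on NNFI and CFI at .90 or higher and RMSEA below .06, as already stated, and report RMSEA with its 90% confidence interval. Under that rule a correct single-group model fails at least one criterion in about 1–8% of samples at alpha .65 and in under 1% at alpha .82, for N = 144 to 180.

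The cost is one sentence. Two incremental indices and RMSEA remain, so no information on fit is lost.
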